8.2 Secondary Outcome Measures

1) HIV outcomes:

- a) HIV-1 RNA viral suppression (plasma HIV-1 RNA pcr < 200 copies/mL) at 16 weeks compared with screening (binary, laboratory assay).
- b) Change in CD4 count at 16 weeks following treatment initiation compared with screening (count; laboratory measurement).

2) Substance Use:

- a) Change in 30 day opioid abstinence (by Addiction Severity Index (ASI)-lite self-report, Time-Line Follow-Back (TLFB) and urine drug screen (UDS) confirmation) in the final 30 days of the 16 week trial compared to screening (binary; laboratory data and self-report).
- b) Change in past 30-day alcohol and other drug use by ASI-lite, TLFB and UDS at week 16 visit, compared to screening (binary; laboratory data and self-report).

3) Engagement in HIV Care:

- a) Change in the proportion of participants prescribed ART within 16 weeks following randomization, compared to baseline (binary; medical record abstraction).
- b) Proportion of participants taking 100% of prescribed ART doses in the past 3 days at 16 weeks for those prescribed ART at any point during the 16 week trial (proportion; self-reported ACTG adherence measure).
- c) Number of HIV primary care visits at 16 weeks (count, chart abstraction).

4) Participant safety:

- a) Change in liver enzymes between screening and week 16 visit (laboratory assay).
- b) Any fatal and non-fatal opioid overdose between screening and week 16 (binary; medical record abstraction and self-report).
- c) Change in Concise Health Risk Tracking score between screening and week 16 visit (continuous; self-report).
- d) Proportion of participants assigned to XR-NTX who develop precipitated opioid withdrawal.

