9.7 Participant Discontinuation

All participants will be followed for the duration of the study (17-24 weeks, depending on length of time required for completion of screening, detoxification, and induction procedures) unless they withdraw consent, or the investigator or sponsor decides to discontinue their enrollment for any reason. Reasons for the investigator or sponsor terminating a participant from the study may include, but are not limited to, the participant becoming a threat to self or others, lack of funding, or DSMB early termination of the study for safety or effectiveness reasons.

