12.6 Clinical Laboratory Tests

Trained staff will be responsible for collecting and processing biologic specimens. Local laboratories at participating pilot sites will be used to conduct laboratory tests. Laboratories must be accredited by the College of American Pathologists (CAP) or equivalent, and participate in the Clinical Laboratory Improvement Act of 1998 (CLIA) or equivalent evidence of laboratory certification. Laboratories will provide reference ranges and proof of laboratory certification.

HIV-1 RNA PCR: will be drawn following randomization, and at 4, 8, 12, and 16 week follow-up visits (or end-of-medication/end-of-treatment if medication or TAU intervention stopped early) for outcomes assessment.

CD4 Count (T-helper cells): will be drawn following randomization and at 4, 8, 12, and 16 week visits (or end-of-medication/end-of-treatment if medication or TAU intervention stopped early) for secondary outcomes assessment.

Peripheral Blood Mononuclear Cells (PBMCs): For all participants, we will collect 4 CPT tubes for PBMC analysis following randomization and at the Week 4 visit or the first blood draw following study drug initiation. PBMC analysis will be conducted in a related NIH application to assess the effects of opioid blockade on TLR mediated immune responses. Samples must be drawn during CTN-0055 study implementation, but may be analyzed at a later time.

Safety labs: AST, ALT, CBC, INR, and urine pregnancy test (for females) will be performed to help determine eligibility at screening. Receipt and review of laboratory test results is necessary before confirming eligibility, conducting randomization and starting study medication. Results of laboratory tests conducted within 30 days prior to randomization (e.g., collected as part of routine detoxification admission) will be acceptable.

Liver profile: (AST, ALT, INR) will be repeated 1 week after study treatment initiation and at 4, 8, 12, and 16 week visits (or end-of-medication/end-of-treatment if medication or TAU intervention stopped early).

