17.5 Analysis of secondary outcomes

The pilot study is small and thus probably under-powered for hypothesis tests. Any conclusions arising from secondary analysis must be regarded as hypothesis-generating only, and need to be validated by independent data. We contemplate no adjustment for multiplicity.

Secondary outcomes will be analyzed as indicated in the italicized text describing each secondary endpoint.

HIV outcomes:

- a) Sustained HIV RNA viral suppression (plasma HIV viral load of < 200 copies/mL) at 16 weeks (*binary, laboratory assay*). *Chi-squared test of independence of sustained viral suppression on treatment assignment.*
- b) Change in CD4 count at 16 weeks following randomization compared with baseline (*count; laboratory measurement*). T-test.

1) Engagement in HIV Care:

- a) Change in the proportion of study participants prescribed ART within 16 weeks following randomization, compared to baseline (*binary; medical record abstraction*). *Each individual can be scored either 0 (not prescribed ART) or 1 (prescribed ART) at both baseline and follow-up, after which his or her outcome score will be the follow-up score minus the baseline score. Outcome scores will be analyzed via rank-based methods such as Wilcoxon rank-sum tests. Covariates can be considered via the cumulative logit model.*
- b) Proportion of participants taking 100% of prescribed ART doses in the past 3 days at 16 weeks for those prescribed ART at any point during the 16 week trial (*proportion; self-reported ACTG adherence measure*). *Chi-squared test comparing proportion to treatment assignment, for those prescribed ART.*
- c) Number of HIV primary care visits at 16 weeks (count, chart abstraction) *outcome scores will be analyzed via rank-based methods such as Wilcoxon rank-sum tests.*

2) Substance Use:

- a) Change in 30 day opioid abstinence (by ASI-lite self-report, TLFB and urine drug screen (UDS) confirmation) in the final 30 days of the 16 week trial compared to baseline (*binary; laboratory data and self-report*). *Analysis using rank-based methods as in outcome 2a.*
- b) Change in past 30day alcohol and other drug use by ASI-lite, TLFB, and UDS at 16 weeks, compared with baseline (*binary; laboratory data and self-report*). *Analysis using rank-based methods as in outcome 2a.*

3) Participant safety, as measured by:

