- a) Change in liver enzymes between baseline and 16 weeks or last lab measurement (*continuous; laboratory assay*). *Analysis via paired t-test, or analysis of change via ordinary least squares.*
- b) Any fatal and non-fatal opioid overdose at 16 weeks (*binary; medical record abstraction and self-report*). *Chi-squared test or logistic regression.*
- c) Change in Concise Health Risk Tracking score at 16 weeks compared to baseline (*continuous; self-report*). *Analysis via paired t-test, or analysis of change via ordinary least squares.*
- d) Proportion of participants assigned to XR-NTX who develop precipitated opioid withdrawal.

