17.6 ITT and Per-Protocol Analyses, Missing Data and Dropouts

Analysis will be ITT in the sense that patients will be analyzed as being members of the arm to which they were originally randomized. We plan no special adjustments for missing data.

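### CD4 is drawn repeatedly for secondary outcomes, but the only stated analysis is an unadjusted t-test on the week 16 change

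*Protocol*

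**What the plan says.** Section 12.6 sets the draws: "CD4 Count (T-helper cells): will be drawn following randomization and at 4, 8, 12, and 16 week visits". The sentence goes on to cover early stoppers and to give the purpose: "or end-of-medication/end-of-treatment if medication or TAU intervention stopped early) for secondary outcomes assessment". The assessment table in section 10.1 marks CD4 at randomization, weeks 4, 12 and 16 and end of treatment, but not at week 8; the HIV-1 RNA row does have week 8.

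Section 17.5, HIV outcomes b), defines the endpoint as "Change in CD4 count at 16 weeks following randomization compared with baseline" and gives the method straight after: "count; laboratory measurement*). T-test". No covariate and no repeated-measures model is named. Section 17.6 states "We plan no special adjustments for missing data".

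Section 8.2 words the same endpoint differently: "Change in CD4 count at 16 weeks following treatment initiation compared with screening". Sections 5.2 and 17.2 also compare with screening.

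Two further passages bear on the reading. Section 17.5 has a fallback for liver enzymes, "Change in liver enzymes between baseline and 16 weeks or last lab measurement", and none for CD4. Section 9.7 intends complete follow-up: "All participants will be followed for the duration of the study", unless consent is withdrawn or enrollment is discontinued.

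**The concern.** Section 5.2 says the secondary objectives exist to produce point estimates comparing XR-NTX with TAU, and section 4.1 says these are to inform a multi-site trial. For CD4 the estimate will come from a single visit, unadjusted for baseline, although earlier values from the same people are scheduled for outcome purposes. Someone with CD4 at weeks 4 and 12 but not at week 16 seems to drop out of the comparison.

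Some missing week 16 values are foreseeable. Section 7.4 bars blood and urine collection at visits with an incarcerated participant. Section 9.2.6 times specimens from treatment initiation, so a randomized person who never initiates has no anchored week 16. Section 6.3 notes that most loss to follow-up in previous XR-NTX trials fell within the first 16 weeks.

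At stake are precision and, under further conditions, bias in the estimate carried forward.

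**Working it through.** **Figures in the plan.** The protocol gives no SD, effect size, precision or missing-data rate for CD4, so there is no CD4 figure to reproduce. Its one precision statement (section 17.2, half-widths within ±0.22) concerns initiation and retention. Everything below rests on assumptions, shown with ranges. The t-test is read as between arms because section 5.2 asks for an arm comparison; section 17.5 does not say so.

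**Step 1: baseline adjustment.** Let ρ be the baseline to week 16 correlation and σ the SD of CD4. Among completers, the change score has variance 2(1−ρ)σ² and the baseline-adjusted value (1−ρ²)σ². The ratio is 2(1−ρ)/(1−ρ²) = 2/(1+ρ).
- ρ = 0.70: 2/1.70 = 1.18
- ρ = 0.82: 2/1.82 = 1.10

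Omitting the adjustment therefore costs about 10-18%, with or without dropout.

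**Step 2: interim visits.** Assume the correlation between visits is r + (1−r)·a^lag, with lag counted in 4-week visits. Assume 20% are missing by week 16, with losses spread evenly over the four follow-up visits and unrelated to CD4. Let p_k be the share whose last visit is k and S_k the covariance, given baseline, of the visits they have. The information is Σ p_k S_k⁻¹, and the variance of the week 16 mean is the last diagonal element of its inverse.

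| r, a | ρ | Baseline part | Interim part | Total |
|---|---|---|---|---|
| 0.6, 0.7 | 0.70 | 1.18 | 1.06 | 1.25 |
| 0.7, 0.6 | 0.74 | 1.15 | 1.05 | 1.21 |
| 0.7, 0.8 | 0.82 | 1.10 | 1.07 | 1.17 |
| 0.5, 0.8 | 0.70 | 1.17 | 1.07 | 1.25 |

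The total is 17-25%. Without a week 8 draw it is 16-24%, so the conflict between sections 12.6 and 10.1 barely matters here. These are large-sample values with the covariance known; simulation at 25 per arm gives 13-23%.

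**Step 3: bias.** Assume SD 250, no true effect, and odds of leaving that rise 1.8-fold per 100-cell fall in observed CD4.
- Dependence in one arm only, with dropout of 20% against 25%: a false completer difference of about 27 cells.
- The same dependence in both arms, with dropout of 15% against 37%: about 24 cells.

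Similar scenarios give 22-28 cells, and higher correlations between visits give less. Using the earlier visits brings the difference to within about 1 cell of zero.

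**Step 4: size against this pilot's uncertainty.** With 25 per arm and 20% missing, 20 per arm remain. The SD of change is 250·√(2(1−ρ)), that is 194 at ρ = 0.70 and 150 at ρ = 0.82. The standard error is SD·√(2/20), that is 61 and 47. With t = 2.02 on 38 degrees of freedom, the 95% half-width is about 124 and 96 cells. A bias of 22-28 cells is 22/61 = 0.4 to 28/47 = 0.6 standard errors.

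**Step 5: when the bias is absent or larger.** A further simulation used 25 per arm, SD of change 100 or 150, and nominal dropout of 10-50%. The t-test rejected 4-7% of the time when dropout was unrelated to CD4, or related to it alike in both arms at similar rates. With dependence on observed CD4 in one arm only, the bias was 19-83 cells and rejection 9-26%, against 3-6% when the interim values were used. When dropout followed the unobserved CD4 course in one arm, rejection was 8-22% for the t-test and 5-12% with the interim values: reduced, not removed.

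**The case against.** The strongest reply is that the unused visits are worth little. Interim values supply only 5-7 points of the gain at 20% missing. In a simulation at 25 per arm they narrow the 95% half-width of a baseline-adjusted completer analysis from about 90-114 to 87-111 cells. This stands, and it is why the missing baseline adjustment is the larger part of the point. Nor does the protocol bar use of the interim draws, so calling them wasted would go too far.

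A second reply is that early stoppers have an end-of-treatment draw and that everyone is to be followed for the full study. This also stands in part: analysis of completers only is an inference from sections 17.5 and 17.6, not a stated rule. But section 17.5 does not say that the end-of-treatment CD4 takes the place of week 16, while it does give such a rule for liver enzymes.

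Third, a reader might infer a much larger loss from the 53% six-month retention in the Russian XR-NTX trial described in section 4.2. At 47% missing the ratios would be 1.34-1.42. The documents do not support that use. The figure is treatment retention over six months in a different population, and stopping treatment is not the same as a missing CD4 at 16 weeks.

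A reader might also infer that the t-test will produce a false arm difference. Nothing in the documents shows that CD4 decline precedes dropout here, or that it does so differently by arm.

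Finally, section 17.5 declares secondary conclusions hypothesis-generating and the pilot probably under-powered. That limits the importance of the point; it does not justify leaving out a nearly free improvement to a planning estimate.

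**Conclusion.** The point holds, at minor severity. Section 17.5 fixes an unadjusted t-test on one visit, section 17.6 plans no missing-data adjustment, and no stated analysis uses CD4 values that section 12.6 schedules for secondary outcomes.

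The precision cost is about 17-25% in participants (13-23% at 25 per arm), given the assumed correlations and 20% missing at week 16. Bias is a possibility, not a finding: it needs dropout that depends on CD4 and differs between arms in strength or rate. At 22-28 cells in the SD 250 scenarios it is small beside the pilot's confidence interval, and it is larger only under harsher assumptions. A model on the observed values removes it if dropout depends on observed CD4 and otherwise only reduces it.

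The endpoint's definition also needs settling. Section 8.2 counts from treatment initiation against screening and section 17.5 from randomization against baseline, while sections 12.6 and 10.1 schedule no screening CD4.

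**What to change.** In section 17.5, HIV outcomes b), replace the t-test with a baseline-adjusted repeated-measures model of CD4 at all scheduled follow-up visits. Terms: arm, visit, arm by visit, baseline CD4 and site. Start from an unstructured covariance and name a simple structure to use if it does not converge with about 50 participants. Report the week 16 arm difference with a 95% CI, and keep the week 16 t-test as a sensitivity analysis.

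In the same edit:
- Enter an end-of-treatment CD4 at the visit nearest its actual date, not as a week 16 value.
- Use the CD4 drawn at randomization as baseline, and reconcile sections 5.2, 8.2, 17.2 and 17.5 on reference visit and time origin. Say how follow-up is timed for randomized participants who never initiate treatment; the model cannot recover anyone with no follow-up CD4.
- Reconcile section 12.6 with the table in section 10.1 on week 8.

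The cost is analysis wording and a few lines of code. The model uses only draws already scheduled.

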12.7 Pregnancy and Birth Control Assessment

This form will document the administration of pregnancy tests, test results, and female participants' self-reports of an acceptable method of birth control. The pregnancy and birth control assessment form, including on-site urine pregnancy tests will be collected at screening. Birth control assessment and a urine pregnancy test will be repeated prior to study drug induction (Week 0), and 1, 4, 8, 12, and 16 week visits (or end-of-medication/end-of-treatment if medication or TAU intervention stopped early). This will correspond to medical visits for repeat study drug dosing (week 0, 4, 8, 12) and week 16 (or end-of-medication/end-of-treatment if medication or TAU intervention stopped early).

12.8 Injection Site Examination

The study clinician will examine the injection site on the next visit following each XR-NTX administration. Participants will be asked to immediately report any injection site reactions to study staff for evaluation, monitoring, and possible referral, as needed. Injection site reactions will be documented on the Injection Site Abnormality Log.

12.9 Pain Assessment

Pain assessment will occur at baseline, 4, 8, 12, and 16 weeks. Participants will be assessed for experiences of pain during the past 4 weeks using the 3-item PEG (Krebs, Lorenz et al. 2009). The PEG asks respondents to estimate on a scale of 0 to 10 their average pain intensity (P), interference with enjoyment of life (E), and interference with general activity (G). Participants will also be asked how pain was managed.

13.0 DRUG USE AND PSYCHOLOGICAL MEASURES

13.1 Urine Drug Screen

Urine drug screens will be collected at screening, study drug induction, week 1 safety visit, and 4, 8, 12, and 16 weeks (or the end-of-medication/end-of-treatment visit if medication or TAU intervention stopped early) for assessment of secondary outcomes. All urine specimens will be collected using FDA-approved one-step temperature-controlled urine drug test cups following all of the manufacturer's recommended procedures. The UDS will test for the presence of the following drugs: opiates, oxycodone, barbiturates, benzodiazepines, cocaine, amphetamines, methamphetamines, marijuana, methadone, buprenorphine and ecstasy (MDMA). The UDS will be performed using three separate testing strips (10Panel, OPI300, and BUP10). In the event urine specimen tampering is suspected, either based on observation or the adulterant tests, study staff should request a second urine sample, directly observed.

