Aim 4: Assess the feasibility of integrating XR-NTX for opioid and alcohol use disorders into HIV clinics. Data collection during study start-up will inform selection of 2 HIV clinics to implement XR-NTX treatment. HIV providers and staff will be trained in detoxification and XR-NTX induction and management. HIV-infected subjects with untreated opioid and/or alcohol use disorders will be randomized to XR-NTX or TAU, followed by detoxification (if needed) and treatment induction. The primary outcomes are 1) treatment initiation (successful treatment initiation of XR-NTX or TAU within 4 weeks of randomization), and 2) retention on treatment condition at 16 weeks. Secondary outcomes include change in 1) HIV-1 RNA viral suppression, 2) Illicit drug and alcohol use, 3) HIV care engagement (receipt of ART, HIV visit adherence, ART adherence), and safety (percent with precipitated withdrawal, hepatotoxicity, or overdose).

Aim 4 Pilot Objective A: Estimate effect size point estimates for rate of treatment initiation and 16 week retention among HIV-infected patients with alcohol or opioid use disorders randomized to XR-NTX vs. TAU.

Aim 4 Pilot Objective B: Estimate effect size point estimates for secondary outcomes of HIV-1 RNA viral suppression, illicit drug and alcohol use, HIV care engagement, and safety among HIV-infected patients with alcohol or opioid use disorders randomized to XR-NTX vs. TAU.

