4.3 Treatment as Usual (TAU)

The current standard of care for treatment of opioid use disorders in HIV clinics is opioid agonist therapy. Recent HIV treatment guidelines recommend office-based BUP/NX or referral for methadone maintenance for HIV-infected patients with opioid use disorders (Thompson, Aberg et al. 2012; Thompson, Mugavero et al. 2012). Through the efforts of the Health Resources and Service Administration (HRSA)-funded Buprenorphine and HIV Evaluation Study (BHIVES) and Substance Abuse and Mental Health Services Administration (SAMHSA)-funded Physician Support Service for Buprenorphine, on-site treatment with office-based buprenorphine is increasingly being offered in HIV clinics. A recent HRSA HIV/AIDS Bureau monogram promotes adoption of office-based buprenorphine in HIV primary care (HIV/AIDS Bureau Special Projects of National Significance Program 2012), see Section 4.1 for evidence of effectiveness of methadone and buprenorphine. Office-based BUP/NX, together with referral for methadone maintenance therapy, is now the standard of care for treatment of opioid use disorders in many U.S. HIV clinics (Thompson, Mugavero et al. 2012).

HIV-infected patients with alcohol use disorders are typically referred for residential, outpatient, and self-help groups (Burnam, Bing et al. 2001; Kraemer, McGinnis et al. 2006). Medication-assisted treatment of alcohol use disorders in HIV clinics is rare.

Many HIV clinics in the U.S., including all those associated with NIDA CTN nodes, receive Ryan White Care Act funding to provide ancillary services for under-insured and uninsured PLWHA. These services typically include on-site case managers, social workers, and substance use counselors who provide critical treatment, referral, and support services for HIV-infected patients with substance use disorders. The site selection process will include a thorough survey of existing treatment services.

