8.0 OUTCOME MEASURES

8.1 Primary Outcome Measures

Primary outcome variables for the CHOICES pilot study are:

- 1) HIV provider willingness to prescribe XR-NTX (Aim 1): HIV provider willingness to prescribe opioid antagonist treatment will be assessed with survey measures adapted from the Medical Opinion Survey (MOS) during the study start-up period (mean; survey data).
- 2) Patient acceptance of opioid antagonist therapy (Aim 2): HIV-infected patient acceptance of opioid antagonist treatment will be assessed with measures adapted from the Medical Opinion Survey (MOS), administered during participant recruitment. Patients will be asked whether they are willing to participate in a trial of XR-NTX vs. TAU (binary; survey data).
- 3) Rate of participant recruitment into trial (Aim 3): This will be used to estimate the speed at which a multisite trial could enroll participants. The number of participants randomized will be assessed on a monthly basis until either 50 participants have enrolled, or 12 months of recruitment have elapsed, whichever comes first (rate; randomization data).
- 4) Treatment initiation (Aim 4A): Treatment initiation is defined as receipt of at least one dose of study medication for those randomized to XR-NTX within 4 weeks of randomization. For those randomized to TAU, treatment initiation will be defined as receiving at least one dose of medication-assisted therapy other than XR-NTX (e.g., buprenorphine for opioid use disorder, disulfiram for alcohol use disorder), or attendance on at least 1 day of non- medication-assisted therapies (e.g., 12-step groups, outpatient rehab referral, etc.) within 4 weeks of randomization. For the TAU group, treatment initiation will be assessed with weekly phone calls from research staff until treatment is initiated or 4 weeks from date of randomization have elapsed, as which point a participant will be considered to have failed treatment initiation (binary; chart review and self-report).

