9.3.4 Treatment as Usual (TAU)

Participants assigned to the TAU group will receive the standard treatment for alcohol and opioid use disorders provided at each HIV clinic. The standard of care in U.S. and Canadian HIV clinics is currently to link with opioid agonist treatment services. Opioid substitution therapy is recommended for HIV-infected participants with opioid dependence (Thompson, Aberg et al. 2012; Thompson, Mugavero et al. 2012), and many HIV practices are being encouraged to adopt clinic-based BUP/NX (HIV/AIDS Bureau Special Projects of National Significance Program 2012). The standard of care for treatment of alcohol use disorders in HIV clinics is referral to detoxification, if needed, as well as outpatient or inpatient rehabilitation programs and 12-step groups, and/or on-site substance abuse counseling services. Medication-assisted treatment of alcohol use disorders with naltrexone, disulfiram, or acamprosate is rare in HIV clinics.

Many HIV clinics receive funding from the Ryan White Care Act for case management and addiction/mental health counseling services to facilitate engagement of HIV-infected patients with substance use disorders in treatment. In a 6-month randomized trial of methadone maintenance referral strategies, passive referral of heroin users resulted in 8% methadone maintenance enrollment at 6 months vs. 29% enrollment among those randomized to case-management assisted referrals ($p = .006$) (Coviello, Zanis et al. 2006).

Methadone maintenance referrals in HIV clinics may more closely approximate case-managed referral enrollment due to the presence of Ryan White Care Act-funded case managers and counselors.

During the formal site selection process, a thorough assessment will be conducted of each site's standard practice for linkage to addiction treatment services. Throughout the course of the trial, HIV clinics will be monitored for any potential changes that might occur in standard practice around linking HIV-infected clinic patients to substance use treatment.

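### Secondary outcome 2a is worded as opioid abstinence, without saying how a urine screen positive for prescribed methadone or buprenorphine is scored; read literally, it biases the comparison toward XR-NTX

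*Protocol*

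**What the plan says.** Protocol Section 8.2 defines substance-use outcome 2a as "Change in 30 day opioid abstinence (by Addiction Severity Index (ASI)-lite self-report", together with the Timeline Follow Back "and urine drug screen (UDS) confirmation) in the final 30 days of the 16 week trial compared to screening". Sections 5.2, 17.2 and 17.5 repeat the opioid-abstinence wording. None of the four limits it to illicit or non-prescribed opioids, lists the analytes that break abstinence, or makes an exception for prescribed agonists. For the analysis, Section 17.5 says only "Analysis using rank-based methods as in outcome 2a".

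The overview names the endpoint differently. Aim 4 in Section 2.1 lists "Illicit drug and alcohol use" among the secondary outcomes. Objective B under that aim and Section 6.1 also speak of illicit use.

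Section 13.1 states that the urine screens serve the secondary outcomes. The panel runs through opiates and oxycodone to "marijuana, methadone, buprenorphine and ecstasy (MDMA".

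On the comparator, Section 4.3 says: "The current standard of care for treatment of opioid use disorders in HIV clinics is opioid agonist therapy". Section 9.3.4 adds: "Opioid substitution therapy is recommended for HIV-infected participants with opioid dependence". In Section 8.1, a dose of medication-assisted therapy counts as successful TAU initiation ("e.g., buprenorphine for opioid use disorder, disulfiram for alcohol use disorder").

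**The concern.** In a trial whose comparator is largely agonist treatment, opioid abstinence and absence of illicit opioid use are different endpoints. Read literally, one buprenorphine prescription is a success on primary outcome 4A and a failure on secondary outcome 2a.

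The change score does not remove the problem. Section 7.2 excludes anyone who received methadone or buprenorphine maintenance in the 4 weeks before screening, so prescribed agonist enters mainly at week 16. It would fall mostly in TAU, because XR-NTX is an antagonist and Section 9.3.3.1 requires an opioid-negative screen before the pre-injection naloxone challenge.

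What is at stake is the effect estimate. Objective B of Aim 4 is to produce point estimates for these outcomes, and Section 4.1 says such estimates are meant to inform the multi-site trial. A definition that shifts the estimate in one direction damages that use even if nobody relies on a p-value. The trial is also unblinded (Section 9.8), which is a reason to fix the scoring rule in advance.

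**Working it through.** The protocol gives no sample size, power or expected rate for opioid abstinence, so there is no figure to reproduce. The check has two parts.

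**1. Wording, side by side**

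| Place in the protocol | What it implies for prescribed agonist |
|---|---|
| 5.2, 8.2, 17.2, 17.5 (outcome 2a) | Opioid abstinence with urine confirmation; no exception stated |
| 2.1 and 6.1 | Illicit use; points away from counting it |
| 13.1 | Methadone and buprenorphine are tested, on screens collected for the secondary outcomes |
| 9.3.3.1 | Names both drugs as opioid agonists next to the negative-screen requirement, for XR-NTX induction only |
| 8.1, outcome 4A | Buprenorphine in TAU is treatment success |
| 13.7 | Use of both drugs is recorded in both arms and supplemented by record review |

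The operative definitions and the overview name different endpoints, and no section supplies the scoring rule that would reconcile them.

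**2. Illustration of size**

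Inputs from the protocol:
- At most 50 participants randomized 1:1, so about 25 per arm (Section 6.1).
- Agonist uptake in other studies: 8% and 29% methadone enrollment in a trial of referral strategies (Section 9.3.4); 41% and 74% engagement in a trial of methadone referral against clinic-based buprenorphine (Section 4.1).

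Assumptions, none given for this trial: the number of TAU participants with opioid use disorder, the true abstinence rate *p*, and that the cited percentages approximate the share *q* on an agonist at week 16.

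*Number on an agonist, 15 TAU participants with opioid use disorder:*
- 15 × 0.08 = 1.2
- 15 × 0.29 = 4.4
- 15 × 0.41 = 6.2
- 15 × 0.74 = 11.1

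That is about 1 to 11. Only those otherwise abstinent would be misclassified. If half are, the numbers halve to 0.6, 2.2, 3.1 and 5.6.

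*Spurious difference.* Let true abstinence be *p* in both arms, and let a share *q* of abstinent TAU participants be on a prescribed agonist and scored as failures. Observed TAU rate = *p*(1 − *q*); spurious XR-NTX advantage = *p* × *q*.

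| *q* | TAU rate, *p* = 0.50 | Advantage (points) | TAU rate, *p* = 0.30 | Advantage (points) |
|---|---|---|---|---|
| 8% | 0.460 | 4.0 | 0.276 | 2.4 |
| 29% | 0.355 | 14.5 | 0.213 | 8.7 |
| 41% | 0.295 | 20.5 | 0.177 | 12.3 |
| 74% | 0.130 | 37.0 | 0.078 | 22.2 |

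*Chance of a false significant result favouring XR-NTX* (two-proportion comparison, two-sided 0.05, *p* = 0.50), for *q* = 8%, 29%, 41% and 74%:
- 25 opioid participants per arm, the most possible: about 5%, 18%, 31% and 83%.
- 12 per arm: about 4%, 11%, 17% and 50%.

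The two-proportion comparison stands in for the planned rank-based test. The two are close if almost nobody is abstinent at screening, since the change score is then nearly binary.

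If prescribed agonist is not scored as use, *p* × *q* drops out and the spurious difference is 0 under the same assumptions.

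**The case against.** The strongest reply is that this is a silence, not an error. Listing an analyte on a test panel is not the same as scoring it as failure. The overview's reference to illicit use, and the treatment of buprenorphine as success in outcome 4A, both suggest that the authors did not mean to penalise prescribed agonists. Analyte-level scoring often sits in a statistical analysis plan, which was not available here, and the data to separate prescribed from other use are collected.

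Much of this stands. A reader might infer that the protocol scores every TAU participant on an agonist as non-abstinent. It does not say so, and participants who also use illicit opioids would be non-abstinent under any rule. A reader might also take the 41% to 74% engagement figures alone and count 6 to 11 of 15 as misclassified. That leaves out the 8% and 29% in Section 9.3.4, which suggests that methadone referral from HIV clinics may come closer to the case-managed figure, 29%. Nor is the effect confined to one arm: analysis is by randomized arm (Section 17.6), and an XR-NTX participant who never starts or who stops could begin an agonist and be scored the same way. Finally, no section ranks 2a as the main substance-use outcome.

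What the reply does not remove is the conflict within the document. The word illicit never reaches the definitions in 5.2, 8.2, 17.2 or 17.5, and those are what an analyst would program from. An analysis plan that followed them faithfully would carry the literal reading forward.

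**Conclusion.** The point holds in conditional form. The overview and the operative definitions of 2a name different endpoints, and the protocol does not settle how a positive result from a prescribed agonist is scored. If the definitions are applied as worded, the estimate is biased toward XR-NTX.

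The size is illustrative only. Under equal true abstinence of 30% to 50% and agonist shares of 8% to 74%, the spurious advantage runs from about 2 to 37 percentage points. With an assumed 15 TAU participants with opioid use disorder, about 1 to 11 would be on an agonist, an upper bound on the number misclassified.

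The reach is limited. Participants with alcohol use disorder only are unaffected, the primary outcomes do not depend on this definition, and Section 17.5 treats secondary results as hypothesis-generating. It is still worth correcting, because the estimate is meant to feed the planning of the next trial.

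**What to change.** In Sections 5.2, 8.2, 17.2 and 17.5, define 2a as no non-prescribed opioid use in the final 30 days and name the analytes that count. State that a methadone or buprenorphine positive, and the matching ASI-Lite or Timeline Follow Back days, are not counted as use when the medication-assisted treatment items (Section 13.7) or the medical record document a current prescription. Apply the same rule in both arms, and to the drug-use part of 2b, which relies on the same screen.

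The cost is one or two sentences in each definition and some linkage of urine, self-report and prescription data already being collected. No visit, assay or treatment changes.
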